6.5 Interim Analysis

Although a specific interim analysis will not be performed as part of this pilot feasibility study, we will include a potential early stop role for an imbalance in mortality between the two groups if there is a difference of more than six deaths in one group compared to the other after enrollment of at least 36 subjects (approximately 18 per group). An imbalance of at least six deaths will provide statistical significance at the level of 0.05 between the two groups. Hospital deaths will be monitored continuously as they occur throughout the course of the study. If the potential early stop rule is reached, the DCC will provide these data to the DSMB for an interim review and consideration to proceed versus terminate the study based on their review of the study data, cause of death, and/or other possible data deemed necessary by the DSMB.

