1 BACKGROUND INFORMATION AND RATIONALE

1.1 Introduction

Approximately 5,000 children die from septic shock each year in the US and thousands more die worldwide.^{1,2} Despite widespread implementation of resuscitation protocols, contemporary studies still report 2-6% mortality for children with septic shock treated in the pediatric emergency department (ED).³⁻⁷ In our recent survey of the Pediatric Emergency Care Applied Research Network (PECARN), 45% of physicians had treated a child for septic shock in the ED who subsequently died in the hospital in the past two years (unpublished data).

Fluid resuscitation is the cornerstone of resuscitation for hypovolemia and shock, and intravenous fluids are among the most commonly used therapies worldwide.^{8,9} Yet, there remains uncertainty as to the most appropriate fluid type to restore effective blood volume and optimize organ perfusion. In the absence of a clear role for the early use of colloids, administration of crystalloid fluids is generally preferred (except in cases of hemorrhage).^{10,11} For septic shock, in particular, crystalloid fluids have long been the standard resuscitative fluid.¹² Crystalloid fluids can be categorized as non-buffered (most commonly 0.9% normal saline [NS]) or buffered/balanced (in the US, this is most commonly lactated Ringer's [LR] solution). NS and LR are inexpensive, stable at room temperature, and nearly universally available with identical storage volumes and dosing strategies. Notably, both are also of proven clinical benefit in septic shock and have extensive clinical experience for use in fluid resuscitation of critically ill patients.⁸ However, while NS is currently used in 80-95% of cases of septic shock,¹³⁻¹⁵ an increasing body of data now suggest that LR resuscitation may have superior efficacy and safety. Buffered crystalloids, including LR, have demonstrated a 1-4% absolute mortality reduction and up to a 50% lower odds of dialysis compared to NS in observational and non-randomized interventional studies in adult sepsis.^{16,17} Nevertheless, because definitive conclusions have not been able to be drawn from existing observational and non-randomized studies, NS overwhelmingly remains the most commonly used fluid based on historical precedent while controversy remains.^{18,19}

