To definitively test the comparative effectiveness of NS and LR, a well-powered randomized controlled trial (RCT) is necessary. A large pragmatic randomized trial embedded within everyday clinical practice provides a cost-efficient and generalizable approach to inform clinicians about best comparative effectiveness of common therapies.²⁰ Unlike explanatory RCTs, pragmatic trials need heterogeneity in patients, non-study therapies, and settings.²¹ To accomplish this, these trials must be large enough to detect small effects and simple enough to incorporate into routine clinical practice. The characteristics of LR and NS provide the ideal scenario for a large pragmatic trial.¹⁸ An ED-based trial is necessary to enroll patients at initiation of resuscitation.^{22,23} While any benefit is expected to be small, even a 1-2% absolute reduction in mortality that is in line with prior adult studies would be a clinically important difference by saving the lives of 50-100 children in the US (and many more worldwide) each year. This overall public health impact is commensurate with changing from NS to LR because such a practice change is a simple, cost-neutral shift from largely using NS to largely using LR.

However, before embarking on a large, pragmatic randomized trial that will determine the comparative effectiveness and safety of NS and LR, several concerns regarding feasibility of such a trial need to be addressed including a) ensuring adequate compliance with study fluid administration within each randomized arm using the proposed pragmatic study design, b) determining that a sufficient proportion of patients can be enrolled using the proposed pragmatic study design that will be embedded within routine clinical practice rather than use of a dedicated study team, and c) demonstrating that the study can feasibly be performed using EFIC when enrolling critically ill infants, children, and adolescents into this clinical trial. If these feasibility criteria can be adequately demonstrated at CHOP as a single site, we will have established the necessary feasibility metrics to indicate a high likelihood of success in a larger, multicenter study that will enroll several thousand patients across the 18 sites comprising Pediatric Emergency Care Applied Research Network (PECARN) to test morbidity and mortality outcomes.

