To our knowledge, only two observational studies comparing NS and LR have been conducted in pediatric septic shock. The first was a propensity-matched analysis of 2,398 patients in the Pediatric Health Information Systems (PHIS) database who received exclusive NS- or LR-based fluid resuscitation for septic shock and was presented in abstract form at the 2016 Society of Critical Care Medicine Annual Congress. The authors reported a 2% lower mortality for children receiving LR versus NS.⁴⁰ The second study, which we recently published in *The Journal of Pediatrics*, was a matched analysis of 4,234 children with septic shock resuscitated with at least some proportion of LR fluid from 382 hospitals in the Premier Healthcare Alliance.⁴¹ Patients were identified using *International Classification of Disease-9-Clinical Modifications* (ICD-9-CM) codes for either severe sepsis/septic shock or a combination of codes indicating infection with organ system dysfunction. Overall, we found no differences in mortality, AKI, or use of renal replacement therapies for patients resuscitated with NS or LR, even when matched by fluid volume and proportion of total fluids given as LR. But for the subset of patients identified using sepsis-specific ICD-9-CM codes (which we and others have previously shown to have more severe illness than patients identified using combination codes), 30-day hospital mortality trended lower in patients who received LR (13.8%) compared to only NS (16.4%; p=0.16), as did the proportion treated with renal replacement therapies (RRT): LR, 1.9% versus NS, 3.9%; p=0.07). However, in our cohort, LR was preferentially used either as first-line fluid in patients with lower illness severity or as an adjunctive fluid in patients who received large amounts of fluid resuscitation, and the matching algorithm was least effective in the most severely ill patients who received the largest total fluid volumes. Consequently, we concluded that the results of our study are best interpreted as establishing the need for and the equipoise to conduct a prospective randomized trial to definitely address the comparative effectiveness of balanced fluids and NS in pediatric sepsis.

Of note, in our recent survey (data unpublished), 95% of PECARN investigators agreed that the existing adult and pediatric data are insufficient to reach consensus on the best crystalloid fluid to use for resuscitation in pediatric septic shock.

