3.3.2 Total Number of Study Sites/Total Number of Subjects Projected

The study will be conducted at one investigative site in the United States (the Children's Hospital of Philadelphia). The University of Utah will act as the Data Coordinating Center (DCC) for this study, but they will not be engaged in human subjects research. Their role is limited to the receipt of a limited dataset from the CHOP investigators.

Recruitment will stop when 70 subjects are enrolled and randomized. It is expected that approximately 80 eligible subjects will be enrolled to produce 70 evaluable subjects.

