9.4.2 Data Safety Monitoring Board (DSMB)

The PRoMPT Bolus – Feasibility study will have a Data Safety Monitoring Board (DSMB) composed of five members from the CHOP/University of Pennsylvania community who have no other involvement in any aspect of the proposed study. Members of the DSMB will be invited by the study investigators in consultation with the DCC. At least one member will be knowledgeable in medical ethics and at least one member will be a patient advocate. The DSMB will have a charter, will approve the protocol prior to implementation, and will meet prior to initiation of subject enrollment, after hospital discharge of the first 36 subjects, and again at the conclusion of the study along with meetings scheduled *ad hoc* as necessary.

The purpose of the DSMB will be to advise the study investigators regarding the continuing safety of study subjects and the continuing validity and scientific merit of the study. The DSMB is responsible for monitoring accrual of study subjects, adherence to the study protocol, assessments of data quality, review of serious adverse events and other subject safety issues, and review of formal statistical analyses. The DCC will send reports relating to these topics to DSMB members ten days prior to each DSMB meeting and will notify the DSMB if the mortality difference exceeds the predetermined stopping rule noted in Section 6.5.

The DCC will remotely staff DSMB meetings and produce minutes of open sessions. Minutes of closed or executive sessions of the DSMB will be produced and retained by the DSMB Chairperson. These closed minutes will not be available outside the DSMB prior to the end of the study.

The DSMB Chairperson will prepare a summary of each DSMB meeting that conveys the public conclusions of the DSMB, with respect to protocol alterations and recommendations concerning continuation of the study. The summary will be provided to the DCC and the DCC will send this summary to all participating investigators for submission to their respective Institutional Review Boards.

The DSMB will meet prior to the start of subject enrollment and then after enrollment of all subjects for this feasibility study. The DSMB, however, will have the discretion to alter meeting timing and frequency, as well as meet ad hoc as necessary throughout the course of the study.

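### Section 6.5 states the mortality trigger with two different thresholds, supports it with a 0.05 claim that is not generally true, and at 2–6% mortality would seldom flag a doubling or tripling of deaths in one arm

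*Combined protocol and SAP*

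**What the plan says.** Section 6.5 plans no formal interim analysis but includes a potential early stopping rule. The rule comes into play "if there is a difference of more than six deaths in one group compared to the other after enrollment of at least 36 subjects", a point the section equates with "approximately 18 per group". Taken literally, this needs a margin of seven. The next sentence gives the rationale with a different margin: "An imbalance of at least six deaths will provide statistical significance at the level of 0.05 between the two groups". It names neither the test nor the sidedness. Deaths are watched continuously. Reaching the margin does not stop the trial; it sends the data to the DSMB, which decides whether to continue.

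Section 9.4.2 relies on the same rule: the DCC "will notify the DSMB if the mortality difference exceeds the predetermined stopping rule noted in Section 6.5".

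For scale, Section 1.1 says that "contemporary studies still report 2-6% mortality for children with septic shock treated in the pediatric emergency department (ED"), and Section 3.3.2 says "Recruitment will stop when 70 subjects are enrolled and randomized". Section 1.3.2.2 reports higher rates in a retrospective subset identified by sepsis-specific codes: "30-day hospital mortality trended lower in patients who received LR (13.8%) compared to only NS (16.4%; p=0.16"). Section 1.1 also regards small effects as important: "even a 1-2% absolute reduction in mortality that is in line with prior adult studies would be a clinically important difference". The documents give no operating characteristics for the rule.

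**The concern.** The two sentences of Section 6.5 cannot both define the rule, so the DCC could not tell whether a margin of exactly six calls for notification. The significance sentence is also the only justification offered for the number chosen, and it describes a single look at one sample size, while the rule is applied continuously up to 70 subjects.

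The margin is large against the deaths to be expected. Most subjects will enter under exception from informed consent. Section 6.3.4 rules out formal comparison of the safety endpoints, and the numeric criteria in Section 4.6.1 apply to individual subjects in the LR arm. The mortality margin is therefore the only numeric comparison between arms that prompts a safety review. A DSMB or IRB reading Section 6.5 could credit it with more sensitivity than it has.

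**Working it through.** **Inputs.** Margin of seven (operative sentence) or six (rationale sentence), active from 36 subjects, continuous monitoring: Section 6.5. 70 randomized, 1:1: Sections 3.3.2 and 3.2, so 35 per arm. Mortality 2–6%: Section 1.1. Higher rates of 13.8–16.4%: Section 1.3.2.2.

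**Step 1: the plan's own figure.** Two-sided Fisher's exact test:

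| Split | 18 per arm | 35 per arm |
|---|---|---|
| 6 vs 0 | p=0.019 | p=0.025 |
| 7 vs 1 | p=0.041 | p=0.055 |
| 8 vs 2 | p=0.060 | p=0.084 |
| 5 vs 0 | p=0.045 | p=0.054 |

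The 0.05 statement reproduces for 6 vs 0 and 7 vs 1 at 18 per arm. It fails for 8 vs 2 at 18 per arm and for 7 vs 1 at full enrollment. Nor is six the smallest significant margin at 18 per arm, since 5 vs 0 already qualifies. The operative margin needs at least 7 vs 0, which gives p=0.008 at 18 per arm. All of these are single-look p-values.

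**Step 2: expected deaths.** Without harm: 70 × 0.02 = 1.4 and 70 × 0.06 = 4.2. With harm in one arm the count rises; at 18% vs 6% it is 35 × (0.18 + 0.06) = 8.4.

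**Step 3: chance that the trigger fires.** Treat subjects as 1:1 pairs, with death probability h in the harmed arm and c in the other. In each pair the running difference rises by 1 with probability h(1−c), falls by 1 with probability c(1−h), and otherwise stays. Check the margin after every pair from the 18th to the 35th and sum the probability of first reaching it. Deaths are assumed to be known at once.

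| Mortality, harmed vs other arm | Margin 7 | Margin 6 |
|---|---|---|
| 4% vs 2% (doubling) | 0.02% | 0.15% |
| 8% vs 4% (doubling) | 0.8% | 2.5% |
| 12% vs 6% (doubling) | 3.9% | 8.9% |
| 6% vs 2% (tripling) | 0.3% | 1.1% |
| 12% vs 4% (tripling) | 5.7% | 12.5% |
| 18% vs 6% (tripling) | 21% | 34% |
| 24% vs 6% (fourfold) | 49% | 64% |

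For margin 7, an even chance of firing needs about 21% mortality against 2%, or about 24% against 6%. Simulation with permuted blocks of four agrees (for example 5.8% at 12% vs 4%). A single final look at 35 per arm gives 3.4% instead of 3.9% at 12% vs 6%.

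**Step 4: a margin of five, for comparison.**

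| Equal mortality in both arms | False alert | | Unequal mortality | Fires |
|---|---|---|---|---|
| 4% | about 1% | | 8% vs 4% | about 7% |
| 6% | about 3% | | 12% vs 4% | about 24% |
| 10% | about 10% | | 18% vs 6% | about 50% |
| 13.8% | about 18% | | | |
| 16.4% | about 23% | | | |

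**Step 5: does the 36-subject start matter?** Changing only the start, from subject 36 to subject 1, moves the simulated firing probability at 12% vs 4% from 5.6% to 5.9% for margin 7, and leaves margin 5 at about 24% (24.4% and 24.3%). These differences are within simulation error or close to it. The threshold drives sensitivity; an earlier start would only let an alert come sooner.

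**The case against.** Several points on the other side stand.

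- A reader might infer from 1.4–4.2 expected deaths that the rule cannot respond to any plausible harm. The documents do not support that: those deaths are expected without harm, and the trigger fires about 21% of the time at 18% vs 6% and 49% at 24% vs 6%. Low sensitivity is the supportable statement.
- A reader might also blame the 36-subject start. Step 5 shows that it hardly affects whether the trigger ever fires.
- Section 6.5 is not the DSMB's only route to mortality data. Section 8.5.1 lists death as an SAE and reports SAEs regardless of relatedness. Section 9.4.2 gives the DSMB review of SAEs and ad hoc meetings. These routes are real but discretionary, and they do not repair the named rule. Section 9.4.2 is also inconsistent on the planned mid-study look: one paragraph schedules a meeting after the first 36 discharges, and a later one lists meetings only before enrollment starts and after it ends.
- If the 13.8–16.4% rates applied, 9.7–11.5 deaths would be expected and margin 7 would fire 35–47% of the time for a doubling. Those rates come from a retrospective subset described as more severely ill. This trial enrolls on clinician suspicion in the ED, which is closer to the setting of the 2–6% figure, but the uncertainty should be shown.
- The protocol says it is not powered for safety, and no death-difference rule in 70 subjects detects a doubling well without many false alerts. That is a reason to state the rule's limits. It is not a reason to leave the threshold ambiguous or resting on a significance statement that does not hold generally.

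**Conclusion.** The concern holds as a matter of internal consistency and of undisclosed low sensitivity. Section 6.5 gives two thresholds, and its 0.05 statement is true for some six-death splits at 18 per arm but not for others, nor for 7 vs 1 at full enrollment. At 2–6% baseline mortality, the operative margin of seven fires less than about 4% of the time for a doubling in one arm and about 0.3–21% for a tripling. A margin of six raises the top of those ranges to about 9% and 34%. A difference of the size Section 1.1 calls important is effectively invisible to either margin: 4% vs 2% gives 0.02% and 0.15%.

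These figures assume 70 subjects, allocation in pairs (block size is not stated), constant mortality within each arm and immediate knowledge of deaths. They depend mainly on baseline mortality. Because the trigger only prompts a review, a false alert costs little, and the documents offer no sound reason for so wide a margin. It does not follow that the trial lacks mortality oversight: SAE review and ad hoc DSMB meetings remain.

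**What to change.** 1. State one threshold in Section 6.5, call it a DSMB-review trigger, and choose it from a stated false-alert limit. The limit is for the sponsor and the DSMB to set; the documents give none.
2. Delete the significance sentence. Print in its place the probability of firing across a range of mortality, including equal mortality at 2%, 4%, 6%, 10% and the Section 1.3.2.2 rates, and doublings and triplings in one arm.
3. Use the same wording in Section 9.4.2 and the DSMB charter, and settle whether the DSMB meets after the first 36 discharges.
4. Say plainly that the rule would miss most doublings of mortality.

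A difference of five or more deaths is one option. Against margin 7 it raises the chance of flagging 12% vs 4% from about 6% to about 24%, and 18% vs 6% from about 21% to about 50%. It still flags 8% vs 4% only about 7% of the time. Starting before subject 36 is optional and affects only how soon an alert can come.

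The cost is wording in two sections and the charter, plus an occasional unnecessary DSMB review. With a margin of five, that chance is about 1–3% if mortality is equal at 4–6%, but about 10% at 10% mortality and about 18–23% at 13.8–16.4%. Sample size and data collection do not change.

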7 STUDY MEDICATION

7.1 Description

Existing hospital supplies of NS and LR will be utilized for this study without any change to packaging or labeling.

7.1.1 Packaging

Both NS and LR will be supplied in their usual bags and/or syringes that are in current use as part of routine clinical practice.

7.1.2 Labeling

Only FDA-approved hospital-issued fluids will be used for this study. The current supply of fluids used at CHOP to be included in this study is NS manufactured by Baxter Healthcare Corporation and LR manufactured by Baxter Healthcare Corporation. Both NS and LR will be labeled as per their existing labels that are in current use as part of routine clinical practice. NS is labeled as “0.9% Sodium Chloride Injection USP” and LR is labeled as “Lactated Ringer’s Injection USP” as part of routine clinical practice. Although an IND will be sought for this study for the purposes of EFIC, since only FDA-approved study fluids that are used as part of routine clinical care for pediatric septic shock (as well as other indications) will be used for this study, no additional labeling will be applied to bags of either NS or LR for the purposes of this study. At CHOP, while NS remains the most common fluid to treat pediatric septic shock in the ED, 50% of the resuscitation fluids used to treat children with septic shock in the pediatric intensive care unit are NS and 50% are LR. Given both NS and LR are commonly used in routine clinical practice and both are FDA-approved, application of study-specific labeling can only contribute to medication errors by altering routine clinical practice. Given the pragmatic nature of the proposed study design that is required to expand this work to the larger PEARN network, enroll several thousand patients, and optimize external validity, it is not practical to employ a dedicated study team to guard against medication errors that may ensue by introducing a non-standardized label on FDA-approved, hospital-issued fluids to be used in this study.

7.1.3 Dosing

Both NS and LR have identical dosing recommendations for use as crystalloid fluid resuscitation in pediatric septic shock, which is 20 mL/kg of body weight administered as rapid IV/IO bolus. Actual doses administered can vary based on clinician preference and/or patient clinical condition. This study will not prescribe a specific dose of either NS or LR to be administered; rather, all dosing decisions will remain at the discretion of the clinical care team with guidance as per existing ED and PICU sepsis pathways (see Appendix 5).

7.1.4 Treatment Compliance and Adherence

Because study fluids can only be given by the clinical care team (rather than self-administered by the patient and/or LAR), there will be no concerns for patient or parent/guardian-related issues with treatment compliance and adherence.

Compliance/adherence with use of study fluid consistent with the randomized arm will be tracked for every patient as part of Aim 1 of this pilot trial. Details of this assessment are described further in Sections 5.2.1 and 5.7.2.

7.1.5 Drug Accountability

The basis of this feasibility study is to establish and test the feasibility of a pragmatic study design that will ultimately be extended to at least 18 sites through the PECARN network and will enroll several thousand patients. Therefore, it is not practical to account for details of fluid administered (including, for example, lot number and residual volume not administered) beyond that which is collected for clinical purposes. Because both NS and LR are already used in common clinical practice at CHOP, are both FDA-approved, and all decisions regarding timing and volume of fluid to be administered will be governed by the treating clinical team (rather than study protocol), no specific study procedures will be established to monitor study fluid accountability. Rather, administration and disposal of residual volumes of both NS and LR will occur as part of routine practice carried out at CHOP. No fluid will be specifically supplied for the purposes of this study since all decisions regarding timing and volume of fluid will be determined by the clinical care team and because there is no meaningful cost differential for the administration of either NS or LR. Thus, because all study patients will receive an efficacious fluid (either NS or LR) to reverse shock without additional fluid-related costs generated by participating in this study, hospital-stocked fluid supplies will be utilized for this study without need for additional accountability beyond routine practice.

